7.4 Other Measures

7.4.1 Screening Assessments

Pre-screen Interview: The pre-screen interview will include questions about pregnancy/postpartum status and enrollment in MOUD treatment.

Demographics: Items from the PhenX Tier 1 of the Substance Abuse and Addiction core²⁸ will be used to collect information on demographic characteristics.

Suicidal and Homicidal Screening Form (PRISM): The Suicide and Homicide Screening Form is a structured, reliable interview modified from the Psychiatric Research Interview for Substance and Mental Disorders- PRISM²⁹ and will be completed by study staff during screening/baseline. A qualified mental health professional must assess participants reporting current suicidal/homicidal intent as specified in the site clinical SOP. For visits held via telemedicine or at an external location, research staff will contact a qualified clinician via phone to coordinate an assessment via telemedicine as quickly as possible; ideally this assessment will occur while the staff and participant are together at the external location.

Treatment and Perinatal Status: The Treatment and Perinatal Status form will be used to assess study candidates' status on study inclusion/exclusion criteria related to pregnancy / postpartum status and enrollment in MOUD treatment.

Prisoner Status: The Prisoner Status form will be used to assess study candidates' status on the study exclusion criterion related to prisoner status.

7.4.2 Sample Characteristics

Substance use history: Participants will be asked the frequency with which they used alcohol, tobacco, and other drugs of abuse during their last active period of use. The wording for the assessment will be taken from the NIDA-Modified ASSIST V2.0, which is a modified version of the World Health Organization Alcohol, Smoking, and Substance Involvement Screening Test.³⁰

7.5 Administrative Forms

Locator Form(s): A locator form is used to obtain information to assist in finding participants during the study. This form is completed at the Screening/Baseline/Randomization visit and collects

contact information including the participant's current address, email address, phone numbers, etc. In order to facilitate locating participants if direct contact efforts are unsuccessful, addresses and phone numbers of family/friends who may know how to reach the participant are collected along with releases of information. No information from locator forms is used in data analyses.

Study Eligibility: This form, which lists all the study inclusion and exclusion criteria, must be completed for every participant who has signed informed consent. Eligible participants will be randomized; ineligible participants will be excluded and deemed screen failures.

Study Intervention Provided: This form must be completed for every randomized participant. The purpose of the form is to capture the elements of the study intervention provided to the participant (e.g., naloxone provided, etc.).

Study Completion: This form, which indicates that the participant has formally terminated his/her study involvement, must be completed for every participant who has been randomized into the study. The purpose of the Study Completion Form is to document: 1) the date on which a randomized participant attended their final study visit, 2) whether the participant completed the study or ended study involvement prematurely, and 3) if the participant ended study involvement prematurely, the reason why that occurred. This form also provides a location for the site PI attestation of review of all study data.

Protocol Deviation: This form should be entered into REDCap whenever a protocol deviation occurs. This form will document a description of the deviation, how it occurred, the corrective action taken to resolve the specific deviation, as well as a description of the plan implemented to prevent future occurrences of similar deviations.

Mental Health Follow-up Assessment: This assessment must be completed by a qualified clinician if the participant endorses suicidality or homicidality in response to the AE assessment. The completion of the Mental Health Follow-up Assessment form requires direct evaluation of the participant for suicide/homicide risk by a qualified mental health professional according to the site's specific SOP. This evaluation will ideally take place prior to the participant leaving the study visit. For visits held via telemedicine or at an external location, research staff will contact a qualified clinician via phone to coordinate an assessment via telemedicine as quickly as possible; ideally this assessment will occur while the staff and participant are together at the external location.

8.0 STUDY PROCEDURES

8.1 Study Overview

The schedule of research visits and research assessments for all participants is delineated in **Table 1**. In accordance with the site's institutional policies and procedures, study visits may occur at other locations affiliated with the institution or elsewhere in the community (including, but not limited to, home visits or visits at non-affiliated community sites), or via remote contact, such as by telephone or other institutionally-approved telemedicine mechanisms. All visits occurring outside of the primary research study site will be managed in such a way that there is no increased risk to participant safety.

8.2 Participant Recruitment, Pre-screening, and Consent

Potential participants will be primarily recruited from existing clients at participating sites. Advertisements may be used, as needed, but all participants must have completed intake at a study site to be eligible for randomization. Interested candidates will complete a pre-screen, which will include questions about pregnancy/postpartum and MOUD treatment status. Candidates who pass the pre-screen will be scheduled for a visit to complete the informed consent, screening/baseline, and randomization. The consent procedure will occur during a live interaction between the candidate and study staff; however, this interaction may occur face-to-face at the study site or at another approved location, or via telemedicine in accordance with institutional policies. If still interested after receiving an explanation of the study, the candidate will be given an opportunity to review, inquire about, and sign the informed consent form. Any participant who has difficulty understanding the information contained in the consent form will be asked to review the misunderstood portion(s) of the consent and discuss them with a research staff member until they show complete understanding of the information and may thus give full consent. Research staff members will work closely with the study candidates in an effort to help them understand the requirements of their participation. Persons with literacy problems will be assisted to the extent possible. Any participant who is unable to demonstrate understanding of the information contained in the informed consent will be excluded from study participation. In the event that the consent procedure occurs via telemedicine, the candidate will provide consent via a HIPAA-compliant electronic system or will be provided with a prepaid shipper/envelope for returning the signed consent to the study team. No other study procedures will occur until the signed consent is received back from the candidate.

8.3 Screening/Baseline

After signing the informed consent form, the study participant will proceed through screening/baseline, which should be completed within a single session.

8.4 Randomization Plan

Eligible participants will be randomized in a 1:1 ratio, stratified by site, to TOME or Control. Research staff will randomize participants to the TOME or Control arm, using REDCap's randomization module; the randomization sequence will be unknown to the research staff.

Table 1: Overview of Assessments and Procedures			
Research Visits	Screen/baseline/ randomization	Week 3 visit	As Needed
Screening Assessments			
Pre-screen interview	X		
Informed Consent	X		
Demographics	X		
Treatment and Perinatal Status	X		
Prisoner Status	X		
PRISM-Suicide/Homicide	X		
Sample Characteristics			
Substance use history	X		
Safety Assessments			
Adverse events		X	
Efficacy Assessments			
Opioid Overdose and Treatment Awareness Survey (OOTAS)	X	X	
Methadone Maintenance Treatment Stigma Mechanisms Scale (MMT-SMS)	X	X	
Thoughts about abstinence	X	X	
Administrative Forms			
Locator information form	X		
Study Eligibility	X		
Study Intervention Provided	X		
Study Completion			X
Protocol Deviation			X
Mental Health Follow-up Assessment			X

8.5 Participant Reimbursement

Participants will be reimbursed for their transportation, inconvenience, and time. The form of this reimbursement will be determined by the study sites. Participants will be reimbursed \$45 for completing screening/baseline and \$30 for completing the Week 3 visit.

8.6 Trial Discontinuation

The study sponsor has the right to discontinue the investigation at any time.

9.0 STUDY TREATMENTS

All randomized participants will be offered naloxone.

9.1 TOME

The TOME intervention is a modified version of the PTOEND intervention.⁵ Modifications include updating the knowledge assessment/education to reflect changes in the drug supply (i.e., the current high prevalence of fentanyl and increasing prevalence of xylazine) and the addition of items specific to pregnancy. Like PTOEND, TOME is a computer-guided intervention which utilizes REDCap³¹ to complete assessments and automatically generate personally-tailored feedback reports; the use of REDCap, which is an NIH-supported, secure, web-based research data platform, limits the technological costs of the intervention to the cost of an internet connection and a computer tablet.

TOME entails a trained RA: 1) administering a REDCap survey to assess an individual's opioid-overdose /MOUD knowledge; and 2) reviewing the personal feedback reports with the recipient. In the present study, the REDCap survey will be administered to all participants at baseline with only the TOME participants receiving the personal feedback reports. Opioid-overdose /MOUD knowledge is assessed with the OOTAS; see Winhusen et al⁴ for information about the survey. In brief, the OOTAS is comprised of 4 sections: 1) opioid-overdose risk factors; 2) signs of an opioid-overdose; 3) how to respond to an opioid-overdose; and 4) misconceptions about MOUD. The first 3 sections include only evidence-based items supported by a literature review, while items for the fourth section were based on both a literature review and on input from the medical staff of the University of Cincinnati-affiliated methadone program. For the present trial, the OOTAS has been modified to include four additional questions: two to assess the participant's knowledge of the increased risk of opioid-overdose with fentanyl and possible increased risk with xylazine and two MOUD knowledge questions specific to pregnancy (i.e., are methadone and BUP recommended during pregnancy and can babies be born addicted as a result of taking methadone or BUP during pregnancy). The Opioid Overdose & Treatment Survey (OOTAS) Feedback Report is generated from the OOTAS and includes a section corresponding to each of the four sections of the OOTAS. The report provides feedback on the questions answered incorrectly by the participant to provide targeted knowledge enhancement, including the correction of misconceptions about MOUD. TOME participants will be offered a copy of their personalized OOTAS Feedback Report; either a physical or electronic copy may be provided.

Training: Trainees will receive a training manual. Training sessions will provide didactic training on the background and rationale of the study, basic listening strategies, a review of the personalized OOTAS Feedback Report, and specific instruction on delivery of the TOME.

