7.0 STUDY MEASURES

7.1 Key Outcome Measures of the Primary Objective

7.1.1 Primary Outcome - MOUD knowledge score

The primary outcome is MOUD knowledge as measured by the Opioid Overdose and Treatment Awareness Survey (OOTAS) knowledge evaluation. The OOTAS is comprised of 4 sections: 1) opioid-overdose risk factors; 2) signs of an opioid-overdose; 3) how to respond to an opioid-overdose; and 4) misconceptions about MOUD.⁴ The OOTAS has been successfully used to measure MOUD knowledge and knowledge change in two published studies^{4,5} and in a small (N=20) pre-post study of recently-enrolled MOUD patients, which found a significant increase in MOUD knowledge after MOUD education ($p<.01$). For the present trial, the OOTAS has been modified to include two additional questions specific to pregnancy (i.e., are methadone and BUP recommended during pregnancy and can babies be born addicted as a result of taking methadone or BUP during pregnancy). The modified OOTAS includes 10 true-false questions to assess MOUD knowledge, yielding a potential score of 0-10.

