7.1.2 Key Secondary Outcome – Opioid-overdose knowledge score

The key secondary outcome is opioid-overdose knowledge as measured by the first three sections of the OOTAS. The OOTAS has been successfully used to measure opioid-overdose knowledge and knowledge change in two prior studies conducted with individuals with OUD. For the present trial, the OOTAS has been modified to include two additional questions to assess the participant's knowledge of the increase risk of opioid-overdose with fentanyl and potential increased risk with xylazine. The modified OOTAS includes 31 true-false questions to assess opioid-overdose knowledge, yielding a potential score of 0-31.

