9.2 Control

Participants randomized to the control condition will be offered three SAMHSA handouts: 1) "Opioid Overdose Prevention Toolkit: Safety Advice for Patients and Family Members";³² 2) "Opioid Overdose Prevention Toolkit: Recovering from Opioid Overdose";³³ and 3) "Medication-Assisted Treatment for Opioid Addiction: Facts for Families and Friends".³⁴ These handouts can be offered as physical copies or electronically.

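### Does the kept TOME feedback report turn the Week 3 OOTAS into an open-book test that favours TOME?

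*Combined protocol and SAP*

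**What the plan says.** All participants complete the OOTAS at baseline, "with only the TOME participants receiving the personal feedback reports" (section 9.1). On content, "The report provides feedback on the questions answered incorrectly by the participant to provide targeted knowledge enhancement". On keeping it, "TOME participants will be offered a copy of their personalized OOTAS Feedback Report; either a physical or electronic copy may be provided".

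Controls are offered three general SAMHSA leaflets, one of them on medication treatment. Section 9.2 adds: "These handouts can be offered as physical copies or electronically". Both arms may therefore keep written material.

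Table 1 (section 8.4) schedules the OOTAS at baseline and again at Week 3. For the primary outcome, section 7.1.1 states: "The modified OOTAS includes 10 true-false questions to assess MOUD knowledge, yielding a potential score of 0-10". Section 7.1.2 states: "The key secondary outcome is opioid-overdose knowledge as measured by the first three sections of the OOTAS"; that score runs from 0 to 31.

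Sections 3.5 and 8.1 prefer the clinic for visits but allow telemedicine, telephone and community locations. Section 12.4 says that participants and staff enter data directly in REDCap. Section 8.5 pays $30 for completing Week 3. Nothing in the protocol says whether reports or handouts are put away during the Week 3 OOTAS.

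**The concern.** One arm receives a document keyed to the outcome items that each person missed; the other receives general leaflets. On a true-false item, learning that an answer was wrong reveals the right one. A TOME participant with the report open at Week 3 could therefore correct answers without having retained anything, and a Control participant could do so less easily. Baseline adjustment cannot remove this, because the baseline survey is completed before the report exists.

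The planned primary difference is small, 0.6 of an item (7.3 against 6.7, section 10.4), so a modest amount of look-up could matter. A knowledge gain is also one of the two findings that section 6.5 names as support for a follow-up trial. Rereading the report before the visit is a legitimate part of TOME and is not in question. The question is only its use during the test.

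**Working it through.** **1. The plan's own figure.** Inputs from section 10.4: N = 120, 88% attending, means 7.3 and 6.7, two-sided alpha 0.05. Per arm, n = 120 × 0.88 / 2 = 52.8. With the post-intervention SD of 1.1, the standard error is 1.1 × √(2/52.8) = 0.214. Then 0.6 / 0.214 = 2.80, and power = Φ(2.80 − 1.96) = 80.0% (79.3% by noncentral t). The stated 80% reproduces. The smallest significant difference is about 1.96 × 0.214 = 0.42 items.

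**2. How much look-up would create the whole planned effect?** Assume no true effect and a mean of 6.7 in both arms.
- Every consulter scores 10/10: 0.6 / (10 − 6.7) = 18% of all TOME completers.
- Half of the missed items are corrected: 0.6 / 1.65 = 36%.

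Section 7.1.1 notes that "the OOTAS has been modified to include two additional questions specific to pregnancy", so the pilot means may come from an 8-item version; the plan does not say. Rescaled by 10/8, the mean is 8.375 and the effect 0.75. The shares become 0.75 / 1.625 = 46% and 0.75 / 0.8125 = 92%.

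**3. Can a consulter reach 10/10?** The report lists only baseline misses. Suppose a person knows 34% of the items and guesses the rest, which gives the plan's Control mean: 3.4 + 6.6/2 = 6.7. The 3.3 misses are in the report. The 3.3 lucky guesses are not, and if guessed again at Week 3 about half are lost. A consulter who uses the report fully then averages 3.4 + 3.3 + 1.65 = 8.35, a gain of 1.65. That equals the half-corrected case, so 36% is the more realistic share in step 2.

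**4. Chance of a significant result favouring TOME when there is no true effect.** Simulated trials, 53 per arm, two-sided t-test at 5%, only TOME participants consulting. The first two result columns span both scale readings and SDs of 1.1 to 1.875.

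| Share of all TOME completers consulting | 10/10 per consulter | Half of misses corrected | Guessing model (step 3) |
|---|---|---|---|
| 0% | about 2.5% | about 2.5% | 2.4% |
| 2% | 3.2–4.7% | 2.7–3.5% | 3.3% |
| 5% | 5.0–9.7% | 3.5–5.5% | 4.6% |
| 10% | 8–24% | 5–11% | 8.2% |

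Look-up is most plausible at remote visits. If 10% of remote participants consult, the overall share is 0.10 × 0.20 = 2% with 20% of visits remote and 0.10 × 0.50 = 5% with half remote. Those are the 2% and 5% rows: roughly 3–5% and 3–10%. The 10% row requires the same rate at clinic visits too.

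If 10% of Controls also consulted and corrected half as much, the 10% row would fall to about 4–8%. If they corrected equally, the excess would vanish.

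**5. Limits.** Every look-up rate, remote share and guessing rate is an assumption; the documents give none. Baseline adjustment was not modelled. By reducing residual variance it could make a given shift somewhat easier to detect.

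**The case for a change.** The strongest case for acting is that every factual link is in the text, that only one arm holds material matched to the outcome items, and that the data checks in sections 12.4 and 16.4 would not detect look-up. One sentence asking for closed materials in both arms, with visit mode recorded, would cost almost nothing, and neither can be recovered reliably after data collection.

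What stands is that the protocol is silent, the asymmetry is real, and a site team would do well to have materials put away. The rest is weaker:

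- **Silence at one level is not an absent procedure.** Section 11.2 refers to an Operations Manual, section 11.17 to training on assessments and visits, and section 12.5 to CRF completion guidelines. None was available for this review, and test administration is ordinarily covered there.
- **No unattended test is described.** Section 9.1 has a trained RA administer the survey at baseline. Section 8.1 presents remote visits as contact by telephone or telemedicine. Section 12.4 is a general statement about all forms and does not say that the Week 3 OOTAS is completed alone.
- **No incentive is apparent.** The Week 3 payment does not depend on the score.
- **The analytic additions gain little.** Visit mode is determined after randomization and the subsets would be small, so a summary by mode could not separate look-up from other differences. Having staff read items aloud in an open-label trial could add cueing and a difference in administration between settings.

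**Conclusion.** The concern identifies missing administrative detail that study staff can be expected to fill sensibly. The plan contains no rule that would produce a wrong result, and no bias has been shown. For look-up confined to remote visits at an assumed 10%, the false-positive rate in TOME's favour is about 3–5% (20% remote) or 3–10% (50% remote) against 2.5%. Under the guessing model it is 3.3% and 4.6%. The figures of 17–24% need 10% of all TOME completers to consult, clinic visits included, each to score 10/10, and the pilot means to be on the 10-item scale. Producing the whole 0.6-item effect would take about 36% of all TOME completers under the more realistic gain.

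The consequence is also bounded. This is a pilot, and section 6.5 looks for lower stigma as well as better knowledge before a follow-up trial; look-up would not directly alter the stigma score. Offering the report is an intended part of TOME. Putting materials away at Week 3 is good practice for the manual or training script, and the protocol, primary model and sample size can stay as they are. The conclusion would need another look only if the Week 3 OOTAS were in fact completed unattended at many remote visits.

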9.2 Control

Participants randomized to the control condition will be offered three SAMHSA handouts: 1) "Opioid Overdose Prevention Toolkit: Safety Advice for Patients and Family Members";³² 2) "Opioid Overdose Prevention Toolkit: Recovering from Opioid Overdose";³³ and 3) "Medication-Assisted Treatment for Opioid Addiction: Facts for Families and Friends".³⁴ These handouts can be offered as physical copies or electronically.

10.0 ANALYTICAL PLAN

10.1 Statistical Hypotheses for Primary Objective

10.1.1 Key Hypotheses

It is hypothesized that the TOME, relative to the control, group will have a greater increase in: 1) MOUD knowledge (primary); and 2) opioid-overdose knowledge (key secondary).

10.1.2 Secondary Hypotheses

It is also hypothesized that the TOME, relative to the control, group will have a significantly greater decrease in: 1) internalized stigma and 2) estimated difficulty in avoiding drug use.

10.2 Intent-to-Treat Participant Population

The intent-to-treat (ITT) population is defined as the participants who are randomized.

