3.5 Assessments

The primary outcome is MOUD knowledge score. The key secondary outcome is opioid-overdose knowledge score. The baseline and 3-week follow-up assessments will ideally occur at the clinic site; however, these visits may occur in whole or in part via telemedicine, at other institutionally-affiliated clinical sites, or elsewhere in the community (including, but not limited to, home visits or other community sites affording appropriate safety and confidentiality) as permitted by the institution and other regulatory bodies.

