3.6 Primary Analysis

Baseline-Week-3 difference in MOUD knowledge will be tested using linear regression at the 5% Type I error rate (two-sided) for the intent-to-treat population.

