6.5 Potential Follow-up Trial

The conceptual model for TOME's hypothesized ability to increase MOUD treatment retention is provided in Figure 2. The present pilot trial is being conducted with active CTN-0080 study sites and is limited to the time remaining for CTN-0080 implementation. As a consequence, the pilot trial is limited to a 3-week follow-up and, thus, is not testing TOME's ability to increase MOUD retention. Instead, this pilot trial is testing TOME's impact on the two hypothesized mediators by which TOME would improve retention. Finding that TOME significantly increases MOUD knowledge and significantly decreases MOUD stigma would provide support for a follow-up trial to test TOME's ability to improve MOUD retention rates.

Fig. 2: Conceptual Model of TOME's Retention Impact

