10.3 Analysis Plan

Each outcome measure will be analyzed for the intent-to-treat population. All statistical tests will be conducted at the 5% Type I error rate (two-sided). All regressions will use outcome as the response variable, treatment (TOME vs. Control) as the covariate of interest, and baseline outcome as a supporting covariate. Site and site-by-treatment will be initially included as supporting covariates and dropped if they are not significant. Baseline-Week-3 continuous outcomes such as the difference in MOUD knowledge will be tested using linear regressions. The Pearson Chi-Square test will be used to test for treatment group differences in AEs.

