10.4 Sample Size Analysis

In our published PTOEND pre-post study we were able to detect a statistically significant increase in opioid-overdose and MOUD knowledge with 80 enrolled participants.⁵ In an unpublished pre-post evaluation of the MOUD education component in patients recently enrolled in MOUD (either buprenorphine or methadone), a sample size of 40 was sufficient to detect a statistically significant increase in mean correct responses from baseline (6.1, SD=1.5) to post-PTOEND (7.3, SD=1.1). Assuming a two-sided test, an $\alpha = .05$, that $\geq 88\%$ of enrolled participants attend the week 3 visit, and mean correct post-intervention responses of 7.3 for the TOME and 6.7 for the Control group, the target sample size of 120 will provide 80% power to detect the difference as statistically significant.

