16.3 Data Management and Analysis

1. **Data acquisition and transmission:** Information will be obtained through REDCap, a web-based electronic data capture and management system. All research staff will be trained in Good Clinical Practice (GCP) guidelines. All data will be de-identified. Only research staff members directly involved with the study will have access to identifying information for the participants.
2. **Data entry methods:** De-identified demographic and clinical data will be managed in REDCap, a software toolset and workflow methodology for collection and management of clinical research data developed by Vanderbilt University, in collaboration with institutional partners including the University of Cincinnati Academic Health Center. Only the necessary study personnel will have access to the database.
3. **Data analysis plan:** All analyses will be completed on the intent-to-treat (ITT) sample using SAS, Version 9.4 (SAS Institute, Inc.). Statistical tests will be conducted at a 5% Type I error rate (two-sided) for all measures. No interim efficacy analyses or adaptive features are planned.

4. Efficacy Analyses:

Each outcome measure will be analyzed for the intent-to-treat population. All statistical tests will be conducted at the 5% Type I error rate (two-sided). All regressions will use outcome as the response variable, treatment (TOME vs. Control) as the covariate of interest, and baseline outcome as a supporting covariate. Site and site-by-treatment will be initially included as supporting covariates and dropped if they are not significant. Baseline-Week-3 continuous outcomes such as the difference in MOUD knowledge will be tested using linear regressions. The Pearson Chi-Square test will be used to test for treatment group differences in AEs.

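### Does the plan need a rule for participants without a Week 3 score, given that every analysis is promised on all randomized participants?

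*Combined protocol and SAP*

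**What the plan says.** Section 10.2 defines the analysis set: "The intent-to-treat (ITT) population is defined as the participants who are randomized". Section 3.6 says the change in MOUD knowledge "will be tested using linear regression at the 5% Type I error rate (two-sided) for the intent-to-treat population". The data and safety monitoring appendix (16.3) adds "All analyses will be completed on the intent-to-treat (ITT) sample".

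Section 10.3 gives the one efficacy model: "All regressions will use outcome as the response variable", with treatment and the baseline value as covariates. Site and its interaction with treatment start in the model and leave it if not significant. AEs are compared by Pearson chi-square.

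In "Table 1: Overview of Assessments and Procedures" (section 8.4), the knowledge, stigma and abstinence measures are taken at baseline and Week 3 only, and AEs at Week 3 only. Section 10.4 assumes that at least 88% "of enrolled participants attend the week 3 visit". No section gives an imputation method, a missing-data assumption or a sensitivity analysis.

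The plan does work to limit loss and to record it. Section 3.5 says "these visits may occur in whole or in part via telemedicine", or elsewhere in the community. Locator contacts are collected (7.5), the Week 3 visit is paid (8.5), reasons for early exit are recorded (7.5), and retention and disposition will be reported (16.8).

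**The concern.** A participant who misses Week 3 has no response value, and there is no intermediate visit to borrow from. Analysing all 120 and fitting this regression cannot both be done literally unless missing scores are filled in, and the plan names no way to do that. Two analysts could therefore report different primary results: one on attenders, the other on all randomized with some fill-in.

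The trial is open-label, so the choice could in principle be made after scores by arm were known. Section 6.5 says a significant knowledge gain, together with a significant fall in stigma, "would provide support for a follow-up trial to test" retention. A switch in significance could bear on that decision. The AE comparison raises a similar question: with all randomized as the denominator, people never assessed at Week 3 count as event-free.

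**Working it through.** **Inputs (section 10.4).** Baseline mean 6.1, SD 1.5; Week 3 means 7.3 (TOME) and 6.7 (Control); two-sided 5% test; 120 randomized; 88% attendance. The power sentence names no SD; 1.1 is the post-intervention SD quoted just before it. Assumed here: SD 1.1 in both arms, a baseline to Week 3 correlation of 0, 0.3 or 0.5, loss at random, and site terms left out.

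**1. Which set does the sample size use?**

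- Per arm, n = 2 × (1.96 + 0.84)² × 1.1² / 0.6² ≈ 52.8, so 53, or 106 in all. 106 / 0.88 = 120.5, which is the plan's 120 to within rounding.
- Power at 53 per arm: 0.6 / (1.1 × √(2/53)) = 2.81; Φ(2.81 − 1.96) = 0.802.
- Power at 60 per arm, all observed: 0.6 / (1.1 × √(2/60)) = 2.99; Φ(2.99 − 1.96) = 0.848.
- Baseline carried forward for 7 per arm: difference 0.53, standard error 0.218; Φ(0.53/0.218 − 1.96) ≈ 0.68.

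The stated 80% reproduces on attenders. It does not reproduce on 120 observed scores or on carried-forward scores.

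**2. What does the model do by default?** It drops records without a response and keeps the rest in their randomized arm. With one follow-up measure, this is valid if attendance is unrelated to the Week 3 score given the covariates in the model. Multiple imputation under the same assumption should then add almost nothing. In simulation (1,500 trials, 30 imputations) it gave a different significance verdict in 1.5% of trials at correlation 0 and 1.0% at 0.5.

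**3. When do the readings part?** At 88% attendance, 120 × 0.12 = 14.4 scores are missing, about 7 per arm. Take baseline carried forward as an illustration; the plan does not name it. The expected gains are 7.3 − 6.1 = 1.2 and 6.7 − 6.1 = 0.6. The 10 v 4 and 4 v 10 splits are assumed.

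| Lost, TOME v Control | Attenders | Carried forward | Verdicts differ (correlation 0 / 0.3 / 0.5) |
|---|---|---|---|
| 7 v 7 | 0.60 | 53/60 × 1.2 − 53/60 × 0.6 = 0.53 | 14% / 11% / 8% |
| 10 v 4 | 0.60 | 50/60 × 1.2 − 56/60 × 0.6 = 0.44 | 28% / 25% / 22% |
| 4 v 10 | 0.60 | 56/60 × 1.2 − 50/60 × 0.6 = 0.62 | 10% / 8% / 6% |

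The 7 v 7 row used 20,000 simulated trials per correlation and the other rows 12,000.

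**4. What could a choice after the fact gain?** With no true effect and 7 v 7 lost, the attender analysis is significant in 4.6% to 4.9% of trials. Taking whichever of the two is significant raises this to 6.1% to 6.5%.

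**5. How robust is the attender result?** Fix the observed difference at 0.60 with 7 v 7 lost and use delta-adjusted multiple imputation. Significance goes only if TOME non-attenders alone fall about 1.35 to 1.75 points below prediction, or if the two arms' non-attenders shift 0.7 to 0.9 points in opposite directions. A fall of 1.35 exceeds the whole expected TOME gain of 1.2: 7.3 − 1.35 = 5.95, below the starting mean of 6.1. A common shift of −1 point gives 0.60 − 7/60 + 7/60 = 0.60. At 10 v 4 it gives 0.60 − 10/60 + 4/60 = 0.50, and at 4 v 10 it gives 0.70.

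**The case for a change.** The strongest case for a change is that the text promises something the model cannot deliver. If attenders are intended, the plan should say so, and a few sentences would do it at no cost in data. The result is also less secure for a smaller effect. On an unadjusted calculation, an observed 0.45 gives p = 0.035 on attenders, but 0.069 with baseline carried forward at 7 v 7 and 0.17 at 10 v 4.

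What stands is that the missing-data rule is unstated. It does not follow that the analysis set is in doubt. The plan names one set throughout and no rival to it. The two approaches consistent with the sample size, attenders and missing-at-random imputation, give practically the same answer. The disagreement at 0.45 comes from a fill-in the documents never suggest. The proposed sentences would record what an analyst would do anyway.

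The AE argument is weaker. Sections 11.16.2 and 16.6 have study staff trained to watch for and report events, and treatment providers monitoring for deterioration, so an event can be known in someone who missed Week 3. Restricting denominators to those assessed at Week 3 could drop exactly that person, for example someone in hospital for suicidal ideation. Showing the number assessed by arm beside the events is ordinary reporting.

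**Conclusion.** No change follows. The plan leaves a detail unstated, and the planned model fills it sensibly: randomized participants with a Week 3 score, in their assigned arm, under missing-at-random given the model covariates. The 80% power rests on that set (0.802 at 53 per arm), and multiple imputation under the same assumption agrees in about 98% to 99% of simulated trials. The disagreements of 6% to 28% belong to a hypothetical carry-forward of baseline. At the planned effect and attendance, it would take an implausibly large shortfall among TOME non-attenders alone, or sizeable opposite shifts in the two arms, to remove significance.

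This rests on SD 1.1 in both arms, a correlation of 0 to 0.5, and loss near the planned 12%. Much heavier loss, strongly unequal loss or a result close to the 5% boundary would call for more caution in interpretation. The retention and disposition figures promised in section 16.8, shown by arm, would let a reader see that.
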